3.3 DATA MONITORING

[figure not shown]
A Roche Internal Monitoring Committee (IMC) will be responsible for the unmasked interim analysis of efficacy for operational/administrative/study related purposes and for safety data monitoring.

The IMC consists of selected Roche representatives including Data Scientist, Safety Representative, and a Clinical Science Representative. The IMC members participating in each meeting will be kept to the minimum required to address the objective of that meeting. The IMC Chair may provide members from other functions access to the

unmasked reports or data. Additional Roche representatives might be involved to produce/process the unmasked listing/data to be analyzed by the IMC.

The organization of the IMC meetings is described in the IMC Agreement.

3.3.1 Safety IMC meetings
The unmasked IMC members that perform regular safety reviews are not part of the RO7200220 project (that is, not part of the Study Management Team, Clinical Expert Feam, or Project Management Team for Study BP43464 and the overall project relating to test product RO7200220).
3.3.2 Efficacy IMC meetings
Efficacy interim analyses to inform possible future development options are foreseen.
They will not influence the conduct of this study.
Furthermore, the sponsor may
perform further interim analyses, as outlined in Section 4.8.
Each interim analysis, will be performed and interpreted by members of the IMC and
appropriate project and management personnel, who would then review aggregate
results by treatment arm and by patient. Access to treatment assignment information will
ollow the Sponsor's standard procedures.
3.3.3 Communication plan for unmasked data monitoring

4. STATISTICAL METHODS

4.1 ANALYSIS POPULATIONS

Population	Description
Treatment-naïve	All randomized participants that are IVT anti-VEGF or periocular/IVT
Intent-to-treat	corticosteroids treatment-naïve as defined in the exclusion criteria 9 and
	10 in the Protocol will be included in the treatment-naïve intent-to-treat
	population. Participants will be grouped according to the treatment
	assigned at randomization. These participants will be selected
	algorithmically depending on specific values in the database.

Population	Description
Previously treated	All randomized participants that are IVT anti-VEGF or periocular/IVT
Intent-to-treat	corticosteroids previously treated participants as defined in the
	exclusion criteria 9 and 10 in the Protocol will be included in the
	previously treated intent-to-treat population. Participants will be grouped
	according to the treatment assigned at randomization. These
	participants will be selected algorithmically depending on specific values
	in the database.
Overall Intent-to-	All randomized participants will be included in the overall intent-to-treat
treat	population. Participants will be grouped according to the treatment
	assigned at randomization. These participants will be selected
	algorithmically depending on specific values in the database.
Per protocol	If a significant number of Protocol Deviations are observed, a per
	protocol population may be used, and will include all
	participants who have received the full number of planned
	administrations of study treatment (12) in the treatment period.
	Participants will be excluded from this per-protocol analysis set if they
	significantly violate the inclusion or exclusion criteria, deviate
	significantly from the protocol, or if data are unavailable or incomplete.
	Excluded cases will be documented together with the reason for
	exclusion. All decisions on exclusions from the analysis will be made
	prior to database closure. Participants will be grouped according to the
	treatment assigned at randomization. These participants will be
	identified algorithmically using the clinical database combined with a
	subjective review of whether protocol deviations are significant or data
	are unavailable or incomplete.
Safety	All participants randomized to study treatment and who received at least
	one dose of the study treatment, whether prematurely withdrawn from
	the study or not, will be included in the safety analysis. Participants will
	be grouped according to the actual treatment received. These
	participants will be identified algorithmically using the clinical database.

Population	Description
Pharmacokinetic	All participants who have received at least one dose of study treatment
	and who have data from at least one post-dose sample will be included
	in the PK analysis population.
Immunogenicity	Participants who had at least one pre-dose or at least one post-dose
	ADA assessment will be included and analyzed according to the
	treatment they actually received or were allocated to receive.
	and reported descriptively via subgroup
	analyses. These participants will be identified algorithmically using the
	clinical database.
ΔDΔ – anti-drug antik	II =interleukin: IVT=Intravitreal O4W=every 4 weeks

ADA = anti-drug antibody, Leaves Leaves LL=interleukin; IVT=Intravitreal, Q4W=every 4 weeks, Q8W=every 8 weeks, PK=Pharmacokinetics, VEGF=Vascular endothelial growth factor

4.2 ANALYSIS OF STUDY CONDUCT

The analysis of study conduct will be based on the overall Intent-to-treat population.

The number of participants randomized will be tabulated by country, site, and treatment arm. Participants disposition (the number of participants randomized, treated, and completing until the primary endpoint timing, as well as the end of study) will be tabulated by treatment arm. Premature study drug discontinuation and study discontinuation, as well as reasons for discontinuations, will be summarized. Eligibility criteria deviations and other major protocol deviations will be summarized by treatment arm. The impact of COVID-19 will be assessed by including major protocol deviations

related to COVID-19 and by summarizing COVID-19 related intercurrent events by treatment arm as necessary.

4.3 ANALYSIS OF TREATMENT GROUP COMPARABILITY

Demographic and baseline characteristics such as age, sex, race/ethnicity and region, and baseline disease characteristics (such as baseline BCVA, baseline DR severity score, ocular assessments, and medical history) will be summarized by treatment as assigned for the treatment-naïve Intent-to-treat population, previously treated Intent-to-treat population, and the overall Intent-to-treat population using means, SDs, medians, and ranges for continuous variables, and counts and proportions for categorical variables, as appropriate.

Exposure to study drug (number of study drug administrations and duration of treatment) will be summarized by treatment group for the safety-evaluable population.

Baseline is defined as the last available measurement obtained on or prior to randomization. Missing baseline assessments will not be imputed.

4.4 EFFICACY ANALYSIS

Efficacy analyses will be based on the treatment-naïve Intent-to-treat, previously treated Intent-to-treat, and overall Intent-to-treat populations unless otherwise defined by estimands.

Unless otherwise noted, analyses of efficacy outcome measures will be stratified by baseline BCVA Early Treatment Diabetic Retinopathy Study (ETDRS) letter score, as assessed on Day 1 (categories: ≤ 38 letters; >38 to <64; ≥ 64) and prior IVT anti-VEGF/corticosteroid therapy (IVT anti-VEGF and/or periocular/IVT corticosteroids treatment-naïve participants vs. previously treated participants).

The stratification factors will be used as recorded in the clinical database and any significant differences to the stratification factors recorded in the IxRS will be noted.

Pairwise comparisons will be performed between the 0.5 mg Ranibizumab IVT Q4W arm (Arm B) and 1.0 mg RO7200220 IVT Q4W and ranibizumab 0.5 mg IVT Q4W (Arm A).

Continuous outcomes will be analyzed using a mixed model for repeated measures (MMRM). Binary endpoints will be analyzed using stratified estimation for binomial

proportions. The estimates and confidence intervals (CIs) will be provided for the mean (for continuous variables) or proportion (for binary variables) for each of the arms and for the difference in means or proportions between pairwise comparisons of the 0.5 mg Ranibizumab IVT Q4W arm (Arm B) and the RO7200220 and ranibizumab arm (Arm A). No formal hypothesis testing will be performed.

4.4.1 Primary Efficacy Estimand

The primary efficacy endpoint is the change from baseline in BCVA averaged over Weeks 44 and 48.

The primary estimand is defined as follows:

- Population(s):
 - Adult participants with DME, who are prior IVT anti-VEGF or periocular/IVT corticosteroids treatment-naive, as defined by the inclusion / exclusion criteria (treatment-naïve Intent-to-treat populationsee Section 4.1)
- Variable:
 - Change in BCVA score from baseline averaged over Weeks 44 and 48.
 BCVA score is based on the ETDRS VA charts assessed at a starting distance of 4 meters.

Intercurrent events:

Row	Intercurrent events	Estimand Strategy
	(the first applicable event from top to	
	bottom takes precedence)	
1	Use of any prohibited systemic treatment or prohibited therapy in the study eye (Section 6.5.3 of Protocol)	A hypothetical strategy will be applied where all values will be censored after the intercurrent event
2	Missed doses or discontinuation of study treatment due to adverse events (AEs) or lack of efficacy	A treatment policy strategy will be applied where all observed values will be used regardless of the occurrence of the intercurrent event.
3	third consecutive missed dose OR discontinuation of study treatment due to reasons other than in Row 2 (e.g. COVID-19, or the rollover to new Protocol versions)	A hypothetical strategy will be applied where all values will be censored after the intercurrent event (the first instance of, if both occur). If more than one dose is given on a particular visit, this only counts as a single missed dose for the purposes of counting numbers of missed doses.
4	Missed dose due to reasons other than in Row 2 (e.g. COVID-19, or the rollover to new Protocol versions)	A treatment policy strategy will be applied where all observed values will be used regardless of the occurrence of the intercurrent event.
5	Death	A hypothetical strategy will be applied where all values will be censored after the intercurrent event.

- Population-level summary

- Difference in adjusted mean between the RO7200220 and Ranibizumab arm (Arm A) and the 0.5 mg Ranibizumab IVT Q4W arm (Arm B).

In the case there are multiple visits within the same visit window and an intercurrent event occurs between these visits, the visits following the intercurrent event will be handled according to the type of intercurrent event as described in the Primary Efficacy Estimand. In the case where the data from the second visit is censored due to the intercurrent event handling, data from the first visit will be used towards the endpoint assessment.

4.4.1.2 Sensitivity Analysis

The following sensitivity analysis using a different handling of missing data will be performed for the primary efficacy endpoint to evaluate the robustness of the primary analysis finding:

a) Treatment policy

The estimand from the primary analysis will be modified to use a treatment policy strategy for all non-death intercurrent events for all available data.

In addition, the intercurrent event definitions and handling strategies from Statistical Analysis Plan version 1 and 2 will be used as a sensitivity analysis. These are displayed below:

Row	Intercurrent events	Estimand Strategy
	(the first applicable event from top to	
	bottom takes precedence)	
1	Use of any prohibited systemic	A hypothetical strategy will be applied where
	treatment or prohibited therapy in the	all values will be censored after the
	study eye (Section 6.5.3 of Protocol)	intercurrent event
2	Missed doses or discontinuation of	A treatment policy strategy will be applied
	study treatment due to adverse events	where all observed values will be used
	(AEs) or lack of efficacy	regardless of the occurrence of the
		intercurrent event.
3	2 or more missed doses OR	A hypothetical strategy will be applied where
	at least one missed dose on	all values will be censored after the
	Weeks 36,40,44 OR	intercurrent event (the first instance of, if
	discontinuation of study	more than one ICE or missed dose).
	treatment	If more than one dose is given on a
	due to reasons other than in Row 2 (e.g.	particular visit, this only counts as a single
	COVID-19, or the rollover to new	missed dose for the purposes of counting
	Protocol versions)	numbers of missed doses.
4	1 missed dose not on Weeks	A treatment policy strategy will be applied
	36,40,44.	where all observed values will be used
	due to reasons other than in Row 2 (e.g.	regardless of the occurrence of the
	COVID-19, or the rollover to new	intercurrent event.
	Protocol versions)	
	,	
5	Death	A hypothetical strategy will be applied where
		all values will be censored after the
		intercurrent event.

4.4.2 Secondary Efficacy Endpoints

A key secondary endpoint is the change from baseline in BCVA averaged over Week 44 and Week 48 in previously treated participants and the overall enrolled population. This endpoint will be analyzed using the estimand, analysis method, and sensitivity analysis as in the Primary Efficacy Endpoint (see Section 4.4.1), with population being the

previously treated Intent-to-treat and overall Intent-to-treat rather than the treatmentnaïve Intent-to-treat population.

Another key secondary endpoint is the Change from baseline in Central Subfield Thickness (CST) averaged over at Weeks 44 and 48. This endpoint will be analyzed using the estimand, analysis method, and sensitivity analysis as in the Primary Efficacy Endpoint (see Section 4.4.1), with population being the previously treated Intent-to-treat, overall Intent-to-treat, and the treatment-naïve Intent-to-treat population, and the variable being the change from baseline in Central Subfield Thickness (CST) as measured by the Central Reading Center averaged over Weeks 44 and 48.

Other secondary endpoints for change in BCVA and CST at other times (in particular, the average over Weeks 20 and 24 and Weeks 32 and 36 in BCVA and Week 24 and Week 36 in CST) will be analyzed reported in a similar way. However, sensitivity analyses will not be required for these.

Change from baseline in BCVA and CST will also be reported using graphical methods. These outputs will be generated separately for the treatment-naïve Intent-to-treat, previously treated Intent-to-treat, and overall Intent-to-treat populations.

Proportions of participants gaining a particular number of letters in BCVA, reaching a particular number of letters in BCVA, reaching a specified CST level, or having absence of intraretinal fluid and subretinal fluid will be reported using tables. These outputs will be generated separately for the treatment-naïve Intent-to-treat, previously treated Intent-to-treat, and overall Intent-to-treat populations.

4.4.3 Other Efficacy Endpoints

The following exploratory endpoints will be summarized using descriptive statistics by including the mean, standard deviation, median, and range for continuous endpoints, and counts and percentages for categorical endpoints, or other listings or tables as appropriate. The handling of intercurrent events (such as the censoring of data following administration of prohibited therapy in study eye) will follow that of the primary efficacy estimand, and outputs will be generated separately for the treatment-naïve Intent-to-treat, previously treated Intent-to-treat, and overall Intent-to-treat populations.

- Proportion of participants with absence of DME (CST <325 µm for Spectralis SD-OCT, or <315 µm for Cirrus SD-OCT or Topcon SD-OCT) over time
- Proportion of participants with absence of intraretinal fluid and/or subretinal fluid over time

[figure not shown]
4.4.4 Subgroup Analyses

The following subgroups may be analyzed with respect to the primary efficacy endpoint using the same method as specified above for each respective endpoint. Forest plots may be presented to summarize the results. The subgroup categories may be combined if there is not enough representation of a specific subpopulation.

- Baseline BCVA Early Treatment Diabetic Retinopathy Study (ETDRS) letter score, as assessed on Day 1 (categories: ≤ 38 letters; > 38 to <64; ≥ 64)
- Prior IVT anti-VEGF/corticosteroid therapy (IVT anti-VEGF and/or periocular/IVT corticosteroids treatment-naïve participants vs. previously treated participants)
- Prior IVT anti-VEGF with/without corticosteroid therapy (IVT anti-VEGF with no
 periocular/IVT corticosteroids previously treated participants vs. IVT anti-VEGF with
 periocular/IVT corticosteroids previously treated participants vs. IVT anti-VEGF
 and/or periocular/IVT corticosteroids treatment-naïve participants)
- Region (North America, rest of the world)
- •
- •
- •
- Age (≤65 years and > 65 years)
- Gender (female and male)
- Race (White, Black or African American, Asian, and other)
- Ethnicity (Hispanic or Latino, Not Hispanic or Latino)
- ADA (positive at some point during study vs negative at all points)

4.5	PHARMACOKINETIC AND PHARMACODYNAMIC ANALYSES

[figure not shown]
1.	
1; 2.	
3.	
2.3.	
1.	
1.2.	
2.	
3.	
PK analyses will be run on the PK population.	

[figure not shown]

4.5.4 Immunogenicity Analysis

4.5.4.1 Immunogenicity Analysis Immunogenicity analyses will be based on the immunogenicity-analysis population as defined in Section 4.1.

4.5.6 Other Analyses

Biomarker exploratory analyses, Population PK/PD analyses, may be

RO7200220—F. Hoffmann-La Roche AG Statistical Analysis Plan BP43445

performed and will be presented separately from the main clinical study report.

4.6 SAFETY ANALYSES

Safety analyses will be based on the safety population. No missing data shall be imputed, and no data shall be censored following intercurrent events. As defined in the safety population, participants will be grouped according to the actual treatment received. In the event that a participant received more than one type of RO7200220 dose, as not intended by protocol, they would be considered in the higher dose level.

Safety will be assessed through descriptive summary of ocular and non-ocular AEs, deaths, and ocular assessments. Clinically significant laboratory abnormalities and clinically significant vital sign and ECG abnormalities will be reported as AEs and evaluated as part of the AE assessments.

Incidence and titer of ADAs to RO7200220 during the study relative to the prevalence of anti-drug antibodies at baseline will be assessed through listings and tables.

At the time of the primary analysis, safety summaries will be summarized based on the complete Week 48 data in the safety population. At the time of the final analysis, safety summaries will be produced based on cumulative Week 72 data in the safety population.

Baseline for safety analyses is defined as the last available measurement prior to first exposure to study drug.

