P Early Treatment Termination (ETT) Visit; If a patient discontinues study treatment prior to Week 44, the ETT visit will be done (if consent still in place). If a decision to discontinue at Week 44 is taken, the regular Week 48 visit should be performed. Patients discontinuing from Study after Week 48 will perform the EOS visit (will be either Week 72 or earlier). Fundus Photography (UWF preferred), Fluorescein Angiography (UWF preferred) and OCT-A should be done if ETT visit ≥ 12 weeks after Day 1.

Legend: ; BCVA=best corrected visual acuity, D=Day, EC=Ethics Committee, ECG=electrocardiogram, EOS= End of study, ETT= early treatment termination, IOP=intraocular pressure, IxRS= interactive voice/web based response system; OCT-A= optical coherence tomography angiography, RBR= Roche Research Biosample Repository, SD-OCT=spectral domain optical coherence tomography, SoC= Standard of Care; UWF=Ultra-wide field, WOCBP=women of childbearing potential.

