4.4 END OF STUDY DEFINITION

A participant is considered to have completed the study if he/she has completed all phases of the study, including the End-of-Study (EOS) visit. The end of the study is defined as the date when the last participant, last observation (LPLO) occurs. LPLO is expected to occur at the EOS visit 4 weeks after the last participant has received SoC treatment in the off-treatment observation period or at Week 72 latest.

5. STUDY POPULATION

The study population consists of male and female participants of ≥ 18 years of age with DM (Type 1 or Type 2) and CI-DME who fulfill all of the inclusion criteria and none of the exclusion criteria.

The study population rationale is provided in Section 4.2.1.

Prospective approval of protocol deviations, also known as protocol waivers or exemptions, is not permitted.

One month is equivalent to a duration of 4 weeks (28 days).

RO7200220 and **RANIBIZUMAB—F. Hoffmann-La Roche Ltd** 38/Protocol BP43464, Version 3

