4.6.1 Exposure of Study Medication

Exposure to study drug (number of study drug administrations and duration of treatment) will be summarized by treatment group for the study eye in the safety-evaluable population.

Duration of treatment is the time from first study drug (RO7200220 and/or ranibizumab) to the earlier of

- Date of study treatment completion
- The analysis cutoff date

Pre-randomization and concomitant systemic medications, ocular medications for the study eye, and ocular medications for the fellow eye will be summarized separately by treatment group.

The following exposure summaries will be presented using tables:

- The average number of doses received as well as the count of patients by doses received of RO7200220 or ranibizumab during the masked treatment period.
- The average AE observation time at each visit.
- The average number of ranibizumab doses received during the off-treatment observation period by each visit.

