4.6.2 Adverse Events

All verbatim AE terms will be coded using the latest version of Medical Dictionary for Regulatory Activities (MedDRA), and the incidence, severity, and seriousness will be summarized by treatment arm.

For safety analyses, unless otherwise specified, only treatment-emergent AEs will be included in the analyses. A treatment-emergent AE is defined as any new AE reported or any worsening of an existing condition on or after the first dose of study drug. Adverse events with missing onset date will be considered to be treatment emergent. Adverse events with partially missing onset date will also be included as treatment emergent when the month (if it was recorded) and the year occur on or later than the month and year of the study treatment start date.

Frequency tables, including participant incidence proportions by treatment arm, will be provided for the events listed below. In addition, graphical presentations will be included, as applicable. For ocular AEs, events in the study eye and fellow eye will be summarized separately.

- Ocular AEs and serious adverse events (SAEs)
- Non-ocular AEs and SAEs
- AEs leading to discontinuation of study treatment
- Treatment related ocular AEs and SAEs as determined by the Investigator
- Procedure related ocular AEs and SAEs as determined by the Investigator
- Intraocular inflammation (IOI)

- Cataract
- Elevated Intraocular Pressure (IOP)
- Infection/Endophthalmitis
- Retinal Detachment
- Retinal vascular occlusive disease

Adverse events associated with suspected or confirmed COVID-19 will also be provided.

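### Final AE tables are crude proportions to Week 72, but AE follow-up after Week 48 appears to end soon after recurrence-triggered standard of care, so the arm comparison may be distorted if time to recurrence differs

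*SAP*

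**What the plan says.** **Analysis.** For the final analysis, SAP Section 4.6 bases the safety tables on "cumulative Week 72 data in the safety population". SAP Section 4.6.2 gives the measure: "Frequency tables, including participant incidence proportions by treatment arm, will be provided for the events listed below". The readable SAP names no person-time rate, time-to-first-event estimate or split by period for these tables. SAP Section 4.6.1 does plan "The average AE observation time at each visit" and a table of off-treatment ranibizumab doses. SAP Section 4.6 also plans a separate Week 48 safety summary at the primary analysis.

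**Follow-up.** Protocol Section 6.1 allows anti-VEGF as SoC in the off-treatment period for participants whose disease recurs. The schedule of activities (Protocol Section 1.3) places SoC at visits from Week 48 to Week 72. Protocol Section 4.4 says "LPLO is expected to occur at the EOS visit 4 weeks after the last participant has received SoC treatment in the off-treatment observation period"; the outer limit is Week 72. Footnote p of the schedule says that those leaving after Week 48 "will perform the EOS visit (will be either Week 72 or earlier"). Protocol Section 8.9.4 adds that SoC given at Week 72 turns that visit into the end-of-study (EOS) visit; the sentence before it is partly redacted. Under Protocol Section 8.3.1, AE collection stops at the earliest of the early treatment termination visit, the EOS visit and Week 72.

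**The concern.** A crude proportion compares arms fairly only if they are observed for similar lengths of time. Here the stopping point after Week 48 appears to be set by recurrence, which is an efficacy outcome that the combination may change. Two arms with the same underlying AE rate could then show different Week 72 proportions because one was watched for longer, or because more of the other received an extra SoC injection.

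The tables at stake include intraocular inflammation, endophthalmitis and retinal vascular occlusive disease, for a new intravitreal combination with safety as a secondary objective. No test is planned, but readers will compare the columns.

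**Working it through.** The documents give no AE rate, recurrence rate or expected follow-up, so there is no figure to reproduce. What follows is an illustration with stated assumptions.

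**Inputs from the documents.** SoC is possible at Weeks 48, 52, ..., 72 (Protocol 1.3). EOS = min(72, SoC week + 4) (Protocol 4.4, applied to each participant by inference from 1.3 and 8.9.4).

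**Assumptions.** Constant first-event hazard λ per year, equal in both arms, from 0.1 to 1.0. Constant probability p of meeting SoC criteria at each visit.

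**Formula.** Crude incidence = Σ w(t) × [1 − exp(−λt/52)], where w(t) is the share of the arm with EOS at week t.

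**Upper bound.** For a participant who completes Week 48, follow-up runs from 52 to 72 weeks (72/52 = 1.38). If all of one arm stopped at 52 weeks and all of the other at 72:

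| λ per year | 52 weeks | 72 weeks |
|---|---|---|
| 0.1 | 9.5% | 12.9% |
| 0.2 | 18.1% | 24.2% |
| 0.5 | 39.3% | 50.0% |

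**Intermediate scenarios.** Worked case for p = 0.10: the shares with EOS at Weeks 52, 56, 60, 64 and 68 are 0.100, 0.090, 0.081, 0.073 and 0.066, and 0.590 reach Week 72, so mean follow-up is 66.7 weeks. For p = 0.30 the shares are 0.300, 0.210, 0.147, 0.103 and 0.072, with 0.168 at Week 72, so the mean is 59.8 weeks.

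| p, Arm A v Arm B | Mean follow-up (weeks) | Crude at λ = 0.2 | Arm A excess, λ = 0.1 to 1.0 |
|---|---|---|---|
| 0.15 v 0.15 | 64.6 v 64.6 | 22.0% v 22.0% | 0 |
| 0.15 v 0.25 | 64.6 v 61.2 | 22.0% v 20.9% | 0.6 to 2.0 points |
| 0.10 v 0.30 | 66.7 v 59.8 | 22.6% v 20.5% | 1.2 to 4.0 points |
| 0.05 v 0.40 | 69.2 v 57.5 | 23.3% v 19.8% | 2.0 to 6.7 points |

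**Counter-case: AEs caused only by injections.** Assume risk r per dosing visit, 12 study visits and at most one SoC injection, with r the same in both arms. Incidence = 1 − (1 − r)^12 × (1 − r·s), where s = 1 − (1 − p)^7 is the share receiving SoC.

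- p = 0.10 v 0.30: s = 0.522 v 0.918. At r = 1%, 11.8% v 12.2%; at r = 3%, 31.7% v 32.5%. Arm A is lower by 0.4 and 0.8 points.
- p = 0.05 v 0.40: s = 0.302 v 0.972. At r = 1%, 11.6% v 12.2%; at r = 3%, 31.2% v 32.6%. Arm A is lower by 0.6 and 1.4 points.

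**After adjustment.** With constant equal hazards, first events per person-time are the same in both arms by construction (20 per 100 person-years at λ = 0.2). A Week 48 cut also gives equality: 1 − exp(−0.2 × 48/52) = 16.9% in both.

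**Limit of a whole-study rate.** Suppose a rare event occurs only during dosing, at equal frequency in both arms. Dividing by mean follow-up of 66.7 v 59.8 weeks gives a rate ratio of 59.8/66.7 = 0.90 for Arm A. The crude ratio in the same scenario at λ = 0.2 is 22.6/20.5 = 1.10. A single rate over the whole study can therefore mislead by a similar amount in the opposite direction, which is why the split by period matters.

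**The case against.** The strongest case against the point has five parts.

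- **Direction.** A reader might infer that the arm with longer benefit will show more AEs. The documents do not support that. It needs a real difference in time to SoC and AEs that accrue with calendar time. Injection-related AEs can reverse the sign, and study-treatment discontinuations cannot arise after dosing has ended. This stands.
- **Evidence for the exit rule.** Protocol 4.4 is worded for the last participant, the participant-level sentence in 8.9.4 is partly redacted, and the recurrence criteria in Section 6.5.1.2 are not in the public text. Early exit after SoC is a sound inference but not a fully visible rule. This stands as a limit on certainty.
- **Size.** The contrast of 52 with 72 weeks needs every participant in one arm to receive SoC at the first possible visit and every participant in the other to stay to the end. It is only a bound. The likelier gaps are also small beside sampling error: at 35% incidence the 95% half-width for a difference is 1.96 × √(2 × 0.35 × 0.65/n), or 13.9 points with 90 per arm and 12.3 with 115. This stands, although a systematic shift does not become harmless because the interval is wide.
- **Already planned.** The observation-time table, the off-treatment dose table and the Week 48 summary will make an imbalance visible. They do not correct the final tables.
- **Person-time rates have their own bias** when the hazard falls after dosing stops. This is correct, and a split by period beside the crude proportions meets it.

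**Conclusion.** The plan as written can mix the Week 72 AE comparison with durability of effect and with post-SoC exposure. Under equal true hazards and the assumed recurrence patterns, the false excess in the later-recurring arm is about 1 to 7 points. For purely injection-driven AEs it is a deficit of about 0.4 to 1.4 points. With equal time to SoC there is no gap. All recurrence and AE rates are assumptions, and the participant-level exit rule is partly inferred.

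A reader might also infer that planned follow-up is equal in all participants up to Week 48, so that the Week 48 table is free of the problem. The documents do not support that fully. SAP Section 2.2 says that the last treatment visit under Protocol Version 1 was Week 20 and that some participants had already entered off-treatment observation under that version. Some of them may have left before Week 48; their schedule is not given. The Week 48 table is still the better between-arm comparison.

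This is a worthwhile, low-cost improvement to descriptive reporting. It does not invalidate the safety analysis.

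**What to change.** In SAP Section 4.6.2, for the final analysis:

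1. Keep the crude participant proportions.
2. Add exposure-adjusted incidence rates by arm with confidence intervals, split into the period to Week 48 and the period after it, with events after SoC shown separately. Time at risk ends when AE collection ends.
3. Name the cumulative Week 48 table as the main between-arm safety comparison.
4. Identify the Protocol Version 1 participants who went off treatment after Week 20, or handle their shorter follow-up through person-time.

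The cost is a few extra tables. AE observation time is already being summarised, and study conduct does not change. The limitation to state with the tables is that a rate pooled over the whole study assumes a roughly constant hazard, so the rates by period should carry the interpretation.
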